3. INTRODUCTION

3.1. Disease Background

Defects in the F8 gene result in haemophilia A, an X-linked blood coagulation disorder. Haemophilia A is a rare disease occurring in approximately 173,000 patients worldwide requiring consumption of 0.875 IU Recombinant Factor VIII per capita annually, based on the most recent figures surveyed by the World Haemophilia Foundation (WHF) (WFO, 2019).

In healthy individuals, FVIII is produced in liver sinusoidal cells and in endothelial cells located outside of the liver throughout the body circulating in the bloodstream in an inactive form in a stable noncovalent complex bound to von Willebrand factor (vWF). F8 gene mutations may be inherited or occur spontaneously without previous family history (Ryu, Park, Yoo, Lee, & Choi, 2015). Various mutations causing haemophilia A result in different levels of factor VIII, which in turn influences bleeding tendency (Soucie et al., 2018).

Haemophilia A occurs in varying severities, defined in the World Federation of Haemophilia (WFH) *Guidelines for the Management of Haemophilia* 2nd Edition (2012) as:

- **Severe (factor levels <1 IU/dl or <1 % of normal)** represent approximately 60% of cases. People with severe haemophilia A experience bleeding following an injury and may have frequent spontaneous bleeding episodes, often into their joints and muscles.
- **Moderate (1-5 IU/dl or 1-5% of normal)** represent approximately 15% of cases. People with moderate haemophilia A tend to have bleeding episodes after injuries. Bleeds that occur without obvious cause are called spontaneous bleeding episodes.
- **Mild (5-40 IU/dl or 5 to <40% of normal)** represent approximately 25% of cases. People with mild haemophilia A generally experience bleeding only after serious injury, trauma or surgery.

The population in this study includes adult males with moderate to severe haemophilia A.

3.2. Treatment Background

Currently approved therapies for haemophilia A include a number of plasma-derived and recombinant human factor VIII replacement products and, more recently, non-factor therapies. Restoration of circulating FVIII to approximately 12% of normal levels has been shown to prevent most spontaneous joint bleeding episodes (den Uijl et al., 2011). FVIII replacement is administered as frequently as 1 to 3 times per week, but breakthrough bleeds and joint disease still occur due to suboptimal adherence, non-ideal factor kinetics, and FVIII inhibitor development (HEMLIBRA, 2017). More recently, a non-factor bispecific antibody (emicizumab) was also approved for the treatment of haemophilia A; potential risks include thrombotic microangiopathy, thrombotic events, and coagulation test interference (Aledort, 2019; Peters & Harris, 2018; Weyand & Pipe, 2019).

PROTOCOL

Title: Safety and Efficacy of Encapsulated Allogeneic FVIII Cell Therapy in Haemophilia A
Study No. SIG-001-121

3.3. Need for New Haemophilia A Treatments

Standard care involves repeat prophylactic or on-demand FVIII products, which can impair quality-of-life and often fail to fully prevent long-term joint disease. In contrast to standard episodic (on-demand) or continuous prophylactic care with factor replacement and non-factor therapies that result in peaks and troughs of FVIII levels, SIG-001 offers the potential to achieve sustained, long-lasting therapeutic levels of FVIII with a laparoscopic procedure, avoiding the need for frequent infusions.

4. INVESTIGATIONAL MEDICINAL PRODUCTS USED IN THIS STUDY

This study involves the use of the investigational medicinal product SIG-001. No comparator or other treatments are being studied.

4.1. SIG-001 Description

SIG-001 is a genetically modified allogeneic cell therapy product designed to be administered via a single laparoscopic procedure into the greater sac of the peritoneal cavity. The primary mechanism of action is sustained secretion of BDD-hFVIII, specifically, replacement of the missing clotting FVIII that is needed for effective haemostasis.

SIG-001 BDD-hFVIII secreting spheres are comprised of a human epithelial cell line (ARPE-19 cells) genetically modified with a transposon-based non-viral vector to express B-domain deleted human factor VIII (BDD-hFVIII). The cells are encapsulated within two-layered modified alginate spheres, which are designed to form a physical barrier protecting cells and spheres from immune damage (e.g. immune rejection and/or pericapsular fibrotic overgrowth, PFO response). SIG-001 spheres consist primarily of alginate, a naturally occurring non-antigenic and biocompatible material with a well-established safety profile. The outer layer alginates are conjugated with a small molecule to protect from PFO, and internal compartment alginates are bonded with a peptide to promote cell adhesion.

Figure 2 Schematic Representation of SIG-001 Study Product

PROTOCOL

Title: Safety and Efficacy of Encapsulated Allogeneic FVIII Cell Therapy in Haemophilia A
Study No. SIG-001-121

4.2. Prior Nonclinical Studies

Use of alginate hydrogels for cell encapsulation has been extensively studied *in vitro* and in animal models, demonstrating no concerning safety signals when used in genetically modified cell therapy systems (Moradali, 2018). Nonclinical studies of SIG-001 conducted by the Sponsor have demonstrated safety and preliminary efficacy (FVIII activity *in vivo*) in mouse and non-human primate (NHP) models without safety concerns. The results of these studies are described in greater detail in the *SIG-001 Investigator's Brochure*.

4.3. Prior Clinical Studies

This is the first-in-human (FIH) clinical study of SIG-001. However, the constituent sodium alginate cell encapsulation approach and genetically modified human ARPE-19 epithelial cell line have been studied clinically for over four decades (Basta et al., 2011; Calafiore et al., 2006; Jacobs-Tulleneers-Thevissen et al., 2013; S. Matsumoto et al., 2014; Tuch et al., 2009).

Intraperitoneal administration of sodium alginate hydrogel spheres -without anti-fibrotic properties- containing encapsulated allogeneic pancreatic islets or porcine pancreatic islets in patients with Type 1 diabetes has resulted in transient improvement in mean blood glucose with no concerning safety issues (Basta et al., 2011; Calafiore et al., 2006; Tuch et al., 2009).

Genetically modified human ARPE-19 cells are in clinical development for the treatment of ophthalmologic protein deficiencies as well as Alzheimer's disease; no concerning safety issues have been reported when administered to humans (Kauper et al., 2012; Mitra, Behbahani, & Eriksdotter, 2019).

4.4. Rationale for the Study

This FIH trial is designed to examine safety and preliminary efficacy of up to 3 doses of SIG-001 in humans. SIG-001 has been evaluated *in vitro* and in animal models to enable sustained secretion of FVIII *in vivo*.

4.5. Risk-Benefit Profile

This Phase 1/2 study has been designed to evaluate the potential risks and benefits associated with SIG-001 administration. Since this study is being conducted in haemophilia A patients, participation may benefit subjects because SIG-001 may result in sustained, long-lasting FVIII levels relative to the peaks and troughs that occur with repeated FVIII administration, but such benefit cannot be guaranteed.

Study participation requires subjects to have a laparoscopic procedure that they would not normally undergo with standard of care; however, this procedure is not expected to pose any risks greater than those of routine diagnostic laparoscopy, and may allow participants to avoid repeated FVIII infusions which inherently pose their own risks. All subjects will be followed for up to five years for safety. The information collected as part of this study is designed to help advance knowledge of SIG-001, which represents a new and potentially long-lasting first-in-class therapeutic option for patients with haemophilia A.

PROTOCOL

Title: Safety and Efficacy of Encapsulated Allogeneic FVIII Cell Therapy in Haemophilia A
Study No. SIG-001-121

5. STUDY OBJECTIVES AND ENDPOINTS

5.1. Study Objectives

5.1.1. Primary Objective

- To evaluate the safety and tolerability of up to 3 dose levels of SIG-001 administered laparoscopically into the greater sac of the peritoneal cavity

5.1.2. Secondary Objectives

- To evaluate development of FVIII inhibitors after administration of SIG-001
- To characterize FVIII activity levels after administration of SIG-001
- To assess frequency of bleeding episodes following SIG-001 administration
- To assess effects of SIG-001 on usage of FVIII products

5.1.3. Exploratory Objectives

- To assess effects of SIG-001 on health and quality-of-life
- To assess the effects of SIG-001 on joint health

5.2. Endpoints

5.2.1. Primary Endpoint

- Clinically significant changes from baseline in vital signs, clinical laboratory tests, and treatment emergent adverse events (TEAEs)

5.2.2. Secondary Endpoints

- Factor VIII inhibitor titres (NBU)
- FVIII activity levels (one-stage and chromogenic assays)
- Bleeding rate (annualized; ABR)
- Total use of factor VIII therapies (annualized)

5.2.3. Exploratory Endpoints

- Summary responses to and change from baseline for EQ-5D-5L and Haem-A-QoL
- Change from baseline in the number of target joints and frequency of bleeding in target joints, as well as change from baseline in joint health using the HJHS assessment

PROTOCOL

Title: Safety and Efficacy of Encapsulated Allogeneic FVIII Cell Therapy in Haemophilia A
Study No. SIG-001-121

6. STUDY DESIGN AND DESCRIPTION

6.1. Study Design

SIG-001-121 is a FIH, phase 1/2, multi-centre, open-label study in escalating dose cohorts to assess the safety, tolerability, and preliminary efficacy of SIG-001 in adults with severe or moderately-severe Haemophilia A without inhibitors. Up to three dose cohorts are planned.

6.2. Study Duration

Total study duration is a maximum of 63 months. This includes up to 90 days for screening and 5 years of follow-up after a single administration of SIG-001.

6.3. Cohorts and Grouping

Up to three (3) escalating dose cohorts are planned. Each cohort will initially include up to three patients and can be expanded to enrol up to three additional patients; thus, up to 6 patients may be enrolled at a single dose level.

- Cohort 1 (Dose 1): CCI of SIG-001 spheres
- Cohort 2 (Dose 2): CCI of SIG-001 spheres
- Cohort 3 (Dose 3): CCI of SIG-01 spheres

For a full description of the rationale for dose selection, refer to Section 6.5.1.

6.4. Dose Escalation Design

Patients will be enrolled in one of 3 escalating dose cohorts. Dosing will be staggered by at least 8 weeks for the first 3 patients enrolled in the study. Thereafter, doses will be staggered by at least 4 weeks for the remaining patients in each dose cohort and between dose cohorts. Cohort expansion does not require staggered enrolment. Following SIG-001 administration, safety and efficacy parameters (FVIII activity) through at least the Week 8 visit (first 3 patients) and at least the Week 4 visit (for the remaining patients in any dose cohort and between dose cohorts) will be reviewed by the Safety Review Committee (SRC) prior to dosing any additional patients (Section 11.1).

Decisions regarding dose escalation will be made by the SRC based on review of safety and FVIII activity data of the preceding patient(s) and/or cohort(s) and the Dose Escalation Decision Tree (Figure 3). Dose escalation will occur only if no dose-limiting toxicities (DLTs) and/or clinically-relevant safety issues have been noted. FVIII activity will be reviewed to inform the dose selection (volume of spheres) for the next cohort.

After the first dose (Dose 1, CCI of SIG-001 spheres), the dose may be increased (e.g. planned Dose 2 & 3) or decreased/de-escalated (Dose -1). No dose increase will be >2-fold higher than a dose level previously found to be safe, and no dose will exceed the maximum dose of CCI.

If any patient achieves FVIII activity >100 IU/dL (equivalent to >100% normal FVIII activity) no further dose escalation will occur. Dosing may proceed at the same level or at a lower level.

PROTOCOL

Title: Safety and Efficacy of Encapsulated Allogeneic FVIII Cell Therapy in Haemophilia A
Study No. SIG-001-121

Cohort 1, Dose 1

If the starting dose in the first patient in Cohort 1, Dose 1 is safe and tolerated and FVIII activity is ≥ 5 IU/dL (equivalent to $\geq 5\%$ normal FVIII activity) at Week 8, the next 2 patients will be administered the same dose and followed for safety and efficacy per the Schedule of Assessments (Table 2 Schedule of Assessments). SIG-001 administration for Patients 2 and 3 will be staggered to include a safety review at least 8 weeks after SIG-001 administration.

If no DLTs or clinically-relevant safety issues occur following safety review of Patient 1 Cohort 1 data but FVIII activity in Patient 1 Cohort 1 is <5 IU/dL at Week 8, dose escalation may occur, and the study will progress to Cohort 2, Dose 2.

Doses will be staggered by at least 8 weeks for the first 3 patients enrolled in the study. Thereafter, doses will be staggered by at least 4 weeks for the remaining patients in any dose cohort and between dose cohorts.

Cohort 2, Dose 2

If the starting dose in the first patient in Cohort 2, Dose 2 is safe and tolerated, the next 2 patients will be administered the same dose via a staggered approach with a safety review after SIG-001 administration, i.e. Dose 2, if:

- 1) FVIII activity in Cohort 2 Patient 1 is ≥ 5 IU/dL, or
- 2) FVIII activity in Cohort 2 Patient 1 is <5 IU/dL but FVIII activity in Cohort 1 Patient 2 or Cohort 1 Patient 3 is ≥ 5 IU/dL

The study will proceed to the highest dose, i.e. Cohort 3, Dose 3, if no DLT or clinically-relevant safety issues occur and:

- 1) FVIII activity in Cohort 1 Patient 1 is <5 IU/dL and FVIII activity in Cohort 2 Patient 1 is also <5 IU/dL, or
- 2) FVIII activity in Cohort 2 Patient 1 is <5 IU/dL, and FVIII activity in Cohort 1 Patients 2 and Patient 3 is <5 IU/dL.

PROTOCOL

Title: Safety and Efficacy of Encapsulated Allogeneic FVIII Cell Therapy in Haemophilia A
Study No. SIG-001-121

Cohort 3, Dose 3

If the starting dose in the first patient in Cohort 3, Dose 3 is safe and tolerated and no DLT or clinically-relevant safety issues occur, the next 2 patients will be administered the same dose via a staggered approach with a safety review after SIG-001 administration, i.e. Dose 3, if:

- 1) FVIII activity in Cohort 3 Patient 1 is ≥ 5 IU/dL, or
- 2) FVIII activity in Cohort 3 Patient 1 is < 5 IU/dL but FVIII activity in Cohort 2 Patient 2 or Cohort 2 Patient 3 is ≥ 5 IU/dL.

[figure not shown]
If FVIII activity in Cohort 3 Patient 1 is < 5 IU/dL and all prior patients had FVIII activity < 5 IU/dL, no further patients will be dosed and enrolment will be stopped. This dose escalation algorithm is intended to monitor patient safety while minimizing patient exposure to subtherapeutic SIG-001 doses. Cohort expansions (up to 3 additional patients) can be initiated after one dose cohort has completed at least 8 weeks of follow-up or after all dose cohorts have completed at least 4 weeks of follow-up. Cohort expansion may be triggered in order to collect additional information regarding safety and efficacy. Decisions regarding cohort expansions will be made by the SRC.

PROTOCOL

Title: Safety and Efficacy of Encapsulated Allogeneic FVIII Cell Therapy in Haemophilia A
Study No. SIG-001-121

Figure 3 Dose Escalation Decision Tree

Note: Dosing will be staggered by at least 8 weeks for the first 3 patients enrolled in the study. Thereafter, doses will be staggered by at least 4 weeks for remaining patients in any dose cohort and between dose cohorts. If any patient achieves FVIII activity >100 IU/dL (equivalent to $>100\%$ normal FVIII activity) no further dose escalation will occur. Dosing may proceed at the same level or at a lower level.

PROTOCOL

Title: Safety and Efficacy of Encapsulated Allogeneic FVIII Cell Therapy in Haemophilia A
Study No. SIG-001-121

6.5. Justification for Dose, Endpoints, and Mitigations

6.5.1. Dose

The starting and maximum SIG-001 doses (mL of spheres) were selected based on nonclinical safety and efficacy (pharmacokinetics). The initially planned doses selected for the study are [REDACTED] As described in Section 4.2, nonclinical toxicology studies have not identified toxicity for SIG-001, and as described in Section 4.3, alginate spheres have been safely administered intraperitoneally to humans at doses known to exceed [REDACTED] and likely up to approximately [REDACTED] Additional details are described in the SIG-001 Investigator's Brochure.

The starting dose of [REDACTED] is expected to be of clinical benefit to participating patients, as supported by the prevention of most spontaneous joint bleeds in haemophilia A patients once FVIII activity rises above 12% (den Uijl et al., 2011). Furthermore, patients achieving the target steady-state FVIII activity for Cohort 1 may be able to discontinue prophylactic FVIII usage, or significantly decrease on-demand FVIII usage.

The starting dose (mL of spheres) for Cohort 1 (Dose 1) was extrapolated from a combination of in vitro and in vivo data to achieve a target steady-state FVIII activity in humans of 0.10 IU/mL (10% of normal hFVIII activity). More specifically, the starting dose volume (mL of spheres) is based on in vivo results of the bioavailability of FVIII produced by different doses of SIG-001 spheres administered IP in rodents, results of in vitro FVIII secretion by individual SIG-001 spheres, the ratio of FVIII secreted by SIG-001 spheres in vitro pre-administration vs. post-administration and the known clearance of a commercially available form of BDD-hFVIII (Mroctocog alfa or BDDrFVIII; trade names ReFacto®, XYNTHA®).

Three ascending dose levels are planned, with a starting dose [REDACTED] of SIG-001 spheres estimated to achieve approximately 0.1 IU/mL plasma level (equivalent to 10% of normal FVIII activity). Estimated steady-state FVIII plasma activity for the planned doses are described in Table 3 below.

Table 3 Estimated FVIII Plasma Activity for Planned Doses

Dose (mL)	Estimated FVIII Plasma Activity ^a
[REDACTED]	6% to 22%
[REDACTED]	11% to 44%
[REDACTED]	17% to 65%

Note (a) [REDACTED] Ranges for estimated plasma FVIII activity by SIG-001 dose volume are based on the estimated range of scenarios tested and physiologically reasonable.

Intraperitoneal administration of alginate spheres to humans in volumes of up to [REDACTED] (reported in the medical literature) and likely, up to [REDACTED] (calculated from reports in the medical literature) have been described; there were no reports of adverse events related to the administered alginate spheres. [REDACTED]

[REDACTED]

The maximum volume of SIG-001 spheres to be administered in this study are approximately up

PROTOCOL

Title: Safety and Efficacy of Encapsulated Allogeneic FVIII Cell Therapy in Haemophilia A
Study No. SIG-001-121

to [REDACTED] (for a 70 kg patient); this maximum volume is below the range of total volumes reported in published clinical experience with alginate spheres and below the nonclinical volumes tested with SIG-001 in 2 species. Additional details are described in the SIG-001 Investigator's Brochure (IB Section 2.1).

[REDACTED]
[REDACTED]

[REDACTED] The maximum volume of buffer corresponding to the highest dose of SIG-001 spheres (Dose 3, up to [REDACTED]) is [REDACTED]; this volume of buffer is expected to be fully absorbed from the peritoneal space in approximately 2.5 to 5 hours post-SIG-001 administration.

6.5.2. Endpoints

Endpoints in this phase 1/2 study examine the safety and preliminary efficacy resulting from up to 3 dose levels of SIG-001 administration in humans, which are not possible to extrapolate from studies in animal models.

The primary endpoint is any clinically significant change from baseline in vital signs, clinical laboratory tests, as well as TEAEs that arise. As this is the first time SIG-001 is being administered to humans, these basic safety considerations are of primary importance. Thus, changes from baseline in safety parameters will be monitored as the primary endpoint of this study.

Secondary endpoints include assessment of (1) FVIII inhibitor titres, (2) FVIII activity levels, (3) annualized bleeding rate, and (4) annualized FVIII therapy use.

Inhibitors limit the therapeutic efficacy of FVIII. There are no good animal models for assessment of inhibitor development. FVIII produced by SIG-001 has a human FVIII amino acid sequence and it is secreted by ARPE-19 cells, a human cell line. Human FVIII produced by SIG-001 is a xenogeneic setting when tested in nonclinical studies, and expectedly results in robust development of FVIII inhibitors in that context. It is unknown how secretion of human FVIII from SIG-001 will affect the inhibitor response to FVIII in humans, but the risk is considered low (Section 6.5.3). Inhibitor titres will be measured at various timepoints using a well-established method, the Nijmegen Bethesda assay.

The goal of SIG-001 administration is to achieve sustained therapeutic levels of FVIII and therefore decrease the risk for spontaneous bleeding episodes and preclude the need for frequent (prophylactic or on-demand) infusions of FVIII. FVIII activity is a well-characterized surrogate marker of clinical benefit and it is currently used in ongoing clinical trials of gene therapy in haemophilia A. As a FIH study, the relationship between SIG-001 dose and FVIII activity is unknown in humans. Therefore, FVIII activity will be evaluated by a central laboratory using two assays, a one-stage clotting assay and a chromogenic substrate assay. Both are standard measures of FVIII activity in a clinical setting.

Annualized bleeding rates and FVIII usage can also inform preliminary efficacy of SIG-001. Patients with haemophilia A with FVIII activity below 2% suffer frequent spontaneous joint bleeds, but annualized spontaneous joint bleeds are close to zero once sustained FVIII activity rises above 12% (den Uijl et al., 2011). A significant reduction in exogenous FVIII usage is

PROTOCOL

Title: Safety and Efficacy of Encapsulated Allogeneic FVIII Cell Therapy in Haemophilia A
Study No. SIG-001-121

expected in patients reaching those FVIII levels. Therefore, data on bleeding rates and FVIII usage after SIG-001 administration will be assessed prospectively throughout the study.

Finally, exploratory endpoints include (1) change in health and quality-of-life as measured by the EQ-5D-5L and Haem-A-QoL instruments, respectively as well as (2) change in the number of target joints and frequency of bleeding episodes in target joints, as well as change in joint health scores as measured by the HJHS instrument. Low health-related quality-of-life is a long-recognized issue in haemophilia patients due to the physical, social, and emotional costs of the disease and the burden of lifelong treatment. It will be important to determine whether SIG-001 is able to impact this important facet of haemophilia patient care. In addition, poorly sustained FVIII levels often result in breakthrough bleeds and subsequent chronic joint disease. The effects of SIG-001 on health, quality-of-life and target joints and joint health will all be monitored as exploratory endpoints.

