7.5.1. Permitted Medications and Therapies

Prior to the laparoscopic procedure, patients will receive a single dose of antibiotic (or a single dose of 2 different antibiotics), per the site's standard clinical practice.

Following the Week 1 visit, patients will be withdrawn from FVIII therapy per the Investigator's discretion. If FVIII therapy is continued after the Week 1 visit, the reason for continuation will be recorded.

On-demand FVIII use is allowed throughout the duration of the study for the treatment of bleeding episodes, perioperative management for surgery or other medical procedures, or preventative for vigorous physical activity. Each use of exogenous FVIII will be recorded and reported during the study.

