7.5.2. Criteria for Re-Starting Prophylactic Therapy

Patients may restart prophylaxis if their FVIII level is <2% normal activity in two separate occasions done at least one week apart after 8 weeks following SIG-001 placement. If a patient needs to restart prophylaxis prior to Week 8, the Investigator should contact the Medical Monitor for approval.

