10.2.2. Bleeding Events and FVIII Usage

The number of bleeding events and quantity of FVIII replacement product used will be collected. At screening, the number of bleeding events and usage of FVIII replacement product will be documented for the past 12 months based on medical history and patient recollection. Bleeding events will be recorded by the patient as part of the patient diary. For each bleeding episode, the following parameters will be recorded: location (joint, muscle, internal organ vs other), type of bleed (spontaneous, traumatic, procedure-related), severity, and action taken/treatment.

Annualized bleeding rate will also be categorized by bleed location (joint, muscle, internal organ, other) and type of bleed (spontaneous, traumatic, procedure-related). Recombinant FVIII replacement therapy during the follow-up period will be recorded by the patient as part of the treatment diary. The following parameters will be recorded for each treatment event: reason for replacement therapy, name of product used, and dose.

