13.5.4. Factor FVIII Product Usage

The annualized use of FVIII replacement products will be calculated for all patients and by dose

PROTOCOL

Title: Safety and Efficacy of Encapsulated Allogeneic FVIII Cell Therapy in Haemophilia A
Study No. SIG-001-121

cohort as the total number of uses of replacement products divided by the length of time on study product follow-up.

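### Annualised total FVIII use (5.2.2, 13.5.4) pools protocol-driven with outcome-driven infusions, so a change in it cannot by itself be attributed to SIG-001

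*Protocol*

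**What the plan says.** Section 6.5.2 puts FVIII use forward as supporting evidence: "Annualized bleeding rates and FVIII usage can also inform preliminary efficacy of SIG-001". It then expects a marked reduction in patients who reach the activity levels cited there. Section 6.5.1 takes the same line: "patients achieving the target steady-state FVIII activity for Cohort 1 may be able to discontinue prophylactic FVIII usage". The effect of SIG-001 on FVIII use is a secondary objective (5.1.2), and annualised total use is the endpoint (5.2.2). Section 13.5.4 fixes the calculation, for all patients and by dose cohort, as the "total number of uses of replacement products divided by the length of time on study product follow-up".

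Other sections decide how much FVIII a patient uses:

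- **9.2.4:** FVIII continues after surgery until the Week 1 visit, possibly once or twice daily.
- **7.5.1:** "Following the Week 1 visit, patients will be withdrawn from FVIII therapy". This is at the Investigator's discretion, and a reason is recorded if FVIII continues.
- **7.5.2:** "Patients may restart prophylaxis if their FVIII level is <2% normal activity in two separate occasions", at least a week apart and after Week 8. Earlier restart needs Medical Monitor approval.
- **7.5.3:** emicizumab is barred unless the restart criteria have been met.
- **7.3:** severe patients may enter on prophylaxis or on demand; moderately severe patients enter on prophylaxis.
- **10.2.2:** each treatment record holds the "reason for replacement therapy, name of product used, and dose", and use over the previous 12 months is documented at screening.

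**The concern.** Sections 6.5.1 and 6.5.2 describe stopping prophylaxis and using less FVIII as things that follow from reaching a FVIII level. In the design, stopping comes first. Until the Week 1 visit, exogenous FVIII holds troughs at 30% or more (9.2.4), and a reading of SIG-001 output alone needs 96 to 168 hours of washout (10.2.1). Withdrawal after that visit therefore cannot rest on measured SIG-001 activity.

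Two of the protocol's thresholds also leave a gap. Section 6.4 uses 5 IU/dL to steer escalation, with the stated aim of limiting exposure to subtherapeutic doses. Section 7.5.2 uses 2% for restart after Week 8. A patient stable at 2 to <5 IU/dL is below the first but does not meet the second, and may go without prophylaxis for most of the year.

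The single count in 13.5.4 adds perioperative, prophylactic, bleed-treatment and pre-activity infusions, across patients who entered on different regimens. At stake is whether a secondary efficacy endpoint can be read as an effect of the product.

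**Working it through.** The protocol gives no figure to reproduce: the analysis is descriptive and 13.5.4 defines only a rate. The check counts Year 1 uses (52 weeks) as 13.5.4 would and compares them with the year before, which 10.2.2 documents.

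**Inputs from the protocol**
- Prior prophylaxis: "FVIII replacement is administered as frequently as 1 to 3 times per week" (3.2), so 52, 104 or 156 uses a year.
- Withdrawal at Week 1; earliest restart under the <2% criterion at about Week 9 or 10.

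**Assumptions**
- Perioperative uses P = 7 to 14 (once or twice daily for one week). Section 13.5.4 does not exclude them.
- Bleeds off prophylaxis: 0 to 40 a year in A and C, 5 to 40 in B, 10 to 40 in D.
- Infusions per bleed: 1 to 2.
- Bleeds on emicizumab: 0 to 5 a year.

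**Formulas** (k = prior uses per week, b = bleeds per year, i = infusions per bleed, r = restart week, e = bleeds per year on emicizumab)
- A, FVIII <2%, FVIII prophylaxis restarted: P + b·i·(r-1)/52 + k·(52-r)
- B, FVIII 2 to <5 IU/dL, no restart: P + b·i·51/52
- C, FVIII <2%, emicizumab from week r: P + b·i·(r-1)/52 + e·i·(52-r)/52
- D, prior on-demand, bleeding unchanged: P + b·i·51/52, against b·i before

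**Examples at 3 a week (156 before)**
- A, low: 7 + 0 + 3×42 = 133, and 133/156 - 1 = -14.7%. High: 14 + 80×8/52 + 3×43 = 155.3, or -0.4%.
- B, low: 7 + 5×51/52 = 11.9, or -92.4%. High: 14 + 80×51/52 = 92.5, or -40.7%.
- C, low: 7, or -95.5%. High: 14 + 80×9/52 + 10×42/52 = 35.9, or -77.0%.

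**Change in total uses, Year 1 against the prior year**

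| Case | 3/week | 2/week | 1/week |
|---|---|---|---|
| A: <2%, FVIII restarted | -15% to about 0% | -12.5% to +8% | -6% to +34% |
| B: 2 to <5, no restart | -92% to -41% | -89% to -11% | -77% to +78% |
| C: <2%, then emicizumab | -96% to -77% | -93% to -65% | -87% to -31% |

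D ranges from +6.8% (80 infusions before, P = 7: 85.5/80) to +138.1% (10 infusions before, P = 14: 23.8/10).

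In B at 1 a week with P = 14, a rise needs more than (52-14)×52/51 = 38.7 bleed infusions a year, for example about 20 bleeds at two infusions each.

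**Does leaving out the perioperative week suffice?** Dropping that week from both numerator and denominator makes D zero, as it should be. In B at 3 a week the rate becomes 5 to 80 a year, and 5/156 - 1 = -96.8% while 80/156 - 1 = -48.7%. The withdrawal effect remains, so the split by reason is still needed.

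**The case against.** The strongest reply is that the protocol claims little. Section 6.5.2 says only that use can inform preliminary efficacy, and it ties the expected reduction to patients reaching stated FVIII levels. Nothing is tested, and activity and bleeding rate are reported beside it. Withdrawal is discretionary, early restart is possible, and detailed tabulations belong in the SAP. Activity held at 2 to <5 IU/dL is generally above entry levels (<1%, or 1 to 2% inclusive), so it is not an absence of effect; 5 IU/dL is an escalation trigger, and no patient-level response is defined.

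Much of this stands and limits the point. Three stronger readings that a reader might infer are not supported:

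- **That total use falls whenever SIG-001 fails.** A patient below 2% is the one who may restart, and case A shows little or no fall. Case D shows a rise.
- **That prophylaxis-free time for 51 of 52 weeks means a 98% fall in the endpoint.** That figure covers prophylactic use only; 13.5.4 also counts perioperative and bleed infusions.
- **That 6.5.2 treats lower use as proof, or that withdrawal is unconditional.** Neither matches the text.

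The appeal to the SAP does not dispose of the point. The protocol itself fixes one pooled quotient and itself offers an efficacy reading of use. Section 13.5.3 specifies a split for bleeds, while 13.5.4 specifies none for use. If the SAP already splits use by reason and regimen, what remains is to align the protocol wording.

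**Conclusion.** The point holds in this form: a change in annualised total FVIII use cannot by itself be credited to SIG-001, because the count combines protocol-driven perioperative dosing and protocol-driven withdrawal with any product effect. In patients who entered on prophylaxis it can fall sharply at 2 to <5 IU/dL (41% to 92% at three a week, but -77% to +78% at one a week) or after a move to emicizumab (31% to 96% across prior frequencies). It changes little on FVIII restart at three a week, and it rises in on-demand patients whose bleeding is unchanged.

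These ranges depend on the assumed perioperative doses, bleed rates and infusions per bleed, and on withdrawal at Week 1 with no early restart. Continued FVIII or early restart would shrink the falls. The protocol does not give the mix of prior regimens that will enrol, so no cohort-level figure can be stated. This is an interpretability problem in a secondary endpoint of a descriptive trial. It is worth correcting because the correction is cheap.

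**What to change.** In 13.5.4:

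- Report annualised use by recorded reason (perioperative or procedure, prophylaxis, bleed treatment, pre-activity) and by prior regimen (prophylaxis or on demand).
- Leave the protocol-driven perioperative period out of the efficacy figure, in both numerator and denominator, and list it separately.
- Show the result beside achieved FVIII activity, with the number of patients resuming prophylaxis and the time to resumption. Show emicizumab separately.
- Note that bleed-treatment use is itself affected by stopping prophylaxis, so it is not a clean substitute for the total.

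In 6.5.1 and 6.5.2, add that a fall in prophylactic use partly follows from withdrawal under the protocol and is not by itself evidence of efficacy.

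The reason for each use and the 12-month history are already collected (10.2.2), so no new data are needed. No withdrawal, restart or escalation rule changes. The cost is a few table rows in small cohorts, where some cells will hold one or two patients, and a less favourable headline figure for FVIII use.
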